### 5.3 Adjustment for Covariates

Efficacy analyses will be adjusted for baseline values and randomization stratum using ANCOVA, MMRM, or Cochran-Mantel-Haenszel tests, where applicable.

### 5.4 Handling of Dropouts, Missing Data, and Data Discrepancies

#### 5.4.1 Missing Duodenal Tissue Eosinophil Count at Week 24

Eosinophil counts will be set to missing if they are collected after subjects have experienced ICE. Subject with missing Week 24 tissue eosinophil count for any reason will be imputed with the eosinophil count collected from the postbaseline unscheduled visit prior to missing. If no eosinophil count is collected postbaseline, the subject will be considered treatment failure for tissue eosinophil response.

#### 5.4.2 Missing Daily PRO Scores at Weeks 23–24

PRO daily scores will be set to missing if they are collected after subjects have experienced ICE. We note that the day before and day of colonoscopy will be taken into consideration when computing baseline and Week 24 TSS scores. For the endpoints of change in the weekly average of PRO TSS, when  $\geq 4$  of 7 daily scores are available, the weekly average score will be calculated using the available daily scores. (See [Appendix 1](#) for justification of allowing weekly

average being calculated from  $\geq 4$  daily scores.) This calculation implies the missing daily scores are the same as the mean of the non-missing daily scores. When  $\geq 4$  daily scores are missing, the weekly score will be set to missing. For the calculation of the average PRO TSS over Weeks 23–24, if  $\geq 1$  weekly score is missing, the biweekly average of Weeks 23–24 will be considered missing.

Missing average of Weeks 23–24 TSS will be imputed using the Markov Chain Monte Carlo (MCMC) method. Baseline tissue eosinophil count and PRO TSS will be included along with the average biweekly PRO TSS (W01\_02, W03\_04, W05\_06, ..., W21\_22, W23\_24) in the multivariate distribution construction. The imputation will be carried out for each treatment group separately and will be executed multiple (50) times (MI). The purpose of MI is to account for the imputation variability in the parameter estimates. An example of the SAS code for this imputation follows.

```
proc mi data=TSS seed=1357986420 nimpute=50
  out=TSS_IMMPUTED ;
  by TRTMT ;
  mcmc chain=multiple impute=full initial=em nbiter=200 niter=100 ;
  var B_EOS B_TSS TSS_W01_02 TSS_W03_04
  ... TSS_W21_22 TSS_W23_24 ;
  run ;
```

After the imputation, the least squares mean (LSM) and standard error (SE) are derived from the conventional ANCOVA from each imputed data set.

These LSM and SE are synthesized to derive the imputation variability-adjusted LSM and SE for each treatment group and for the between treatment difference. These synthesized LSM and SE are then used in the hypothesis test for the between treatment difference. An example of the SAS code for the synthesized LSM comparisons between treatment is as follows.

```
ods output ParameterEstimates=LSMDIF ;
proc mianalyze data=DIFF alpha=0.05 ;
 modeleffects LSM ;
  stderr SE ;
run ;
```

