### 3.5 Determination of Sample Size

A total of approximately 80 subjects will be enrolled.

**First Co-Primary Endpoint:** A sample size of 40 subjects per treatment group will have >90% power to demonstrate a greater proportion of histologic responders at Week 24 in AK002 subjects compared to placebo subjects, assuming the proportions of histologic responders are 0.6 and 0.1 in AK002 and placebo groups, respectively.

**Second Co-Primary Endpoint:** A sample size of approximately 40 patients per treatment group will provide 80% power to detect a statistically significant difference of 7.4 points between AK002 and placebo in the mean reduction from Baseline in TSS at Weeks 23-24, assuming a common standard deviation of 12.5 points (AK002-003 data on file).

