## 5.8 Multiple Comparisons/Multiplicity Adjustment

To control for the family-wise type-I error rate, the following testing procedures will be implemented:

Test each co-primary efficacy endpoint at 2-sided  $\alpha=0.05$  level.

- If  $p \leq 0.05$  for both co-primary endpoints, then reject the null hypothesis that AK002 is no different from placebo and accept the alternative hypothesis that AK002 is superior to placebo in reducing tissue eosinophil count and TSS score.
- If  $p \leq 0.05$  for both co-primary endpoints, the hypothesis tests for the secondary endpoints will proceed in the prespecified order.
- If  $p > 0.05$  for either co-primary endpoint, the null hypothesis is accepted. No hypothesis test will be performed for the secondary endpoints.
- The issue of multiplicity of secondary endpoints will be handled by statistical testing of these outcomes in a hierarchical fashion. The order of secondary endpoints is described in Section 2.2. If at any point during the analysis of the secondary endpoints, the statistical test is not significant at 2-sided  $\alpha=0.05$  level, the hypothesis testing procedure will stop. AK002 will be deemed superior to placebo for all endpoints prior to the stop.

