### 6.11.5 Sensitivity Analyses of the Second Co-Primary Endpoint

The two sensitivity analyses planned below are constructed based on the already imputed biweekly data set from Section 5.4.2.

The first sensitivity analysis is based on the placebo-based pattern-mixture model for the missing data imputation under the missing not at random (MNAR) assumption. In this model, subjects from the active treatment group after the ICE are assumed to behave like the subjects from the placebo group. Their missing data are imputed using the response profile from the placebo subjects who have similar baseline covariates and prior response trajectory. The sample SAS code follows.

```

/*Step 1: Achieve Monotone Missing Data Pattern */

proc mi data=tss seed=135791 nimpute=50 out=mono;
  var B_EOS B_TSS TSS_W01_02 TSS_W03_04 ... TSS_W21_22
  TSS_W23_24;
  MCMC impute=monotone nbiter=200 niter=100;
  By TRTMT;
run;

/*Step 2: Achieve Control-Based Copy-Reference Imputation */

proc mi data=mono seed=135791 nimpute=50 out=outm1;
  class TRTMT;
  by _imputation_;
  var TRTMT B_EOS B_TSS TSS_W01_02 TSS_W03_04 ... TSS_W21_22
  TSS_W23_24;

```

```

monotone reg;
mnar model(TSS_W01_02 TSS_W03_04 ... TSS_W21_22 TSS_W23_24 /
modelobs=(TRTMT='0')); * CODE 0 IS FOR PLACEBO GROUP ;
run ;

/*Step 3: Run MMRM Analysis on Imputed Data */

proc mixed data=tss method=reml;
class TRTMT USUBJID AVISITN ANALYSIS_CENTER GENDER;
model CHG= B_TSS TRTMT AVISITN ANALYSIS_CENTER GENDER
TRTMT*AVISITN B_TTS*AVISITN / DDFM=KR;
REPEATED AVISITN / SUBJECT=USUBJID (TRTMT) TYPE=UN;
RANDOM ANALYSIS_CENTER;
LSMEANS TRTMT*AVISITN / PDIFF CL;
ESTIMATE 'PBO VS. AK002 at WEEKS 23-24' TRTMT -1 1
TRTMT*AVISITN 0 0 0 0 0 0 0 0 0 0 -1
0 0 0 0 0 0 0 0 0 0 0 1 / CL;
ODS OUTPUT PARAMETERESTIMATES=PESTIMATES;
RUN;

/*Step 4: Combining estimates from each imputed data set */

proc mianalyze data=PESTIMATES;
modeleffects ESTIMATE;
stderr stderr;
by label;
ods output PARAMETERESTIMATES=miparm;
run ;

```

The second sensitivity analysis is based on ANCOVA using the imputed data set (Section 5.4.2). The LS mean, SE, and 95% CI for each treatment group and for the between group difference will be derived from ANCOVA with treatment as factor, baseline PRO TSS (continuous) as covariates. The hypothesis test for the treatment effect will be carried out by the F-test. The synthesizing method will be used to combine the results from multiple imputations. The sample SAS code follows.

```

/** ANCOVA by imputation **/

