### 6.12.5 Change in Weekly TSS Over Time

Prior to the analysis, the missing weekly TSS scores will be imputed similarly to the imputation for the missing biweekly PRO TSS scores (Section 5.4.2). The imputed data sets will be analyzed using the mixed model for repeat measures (MMRM) similar to the analysis for the second co-primary endpoint.

The rationale for using the MMRM model is that this analysis is appropriate assuming subjects with missing data behave similarly to other subjects in the same treatment group. Having included in the model baseline symptom score (TSS), and response trajectory prior to missing, it is reasonable to believe that the missing data are either completely at random (MCAR) or at random (MAR) in this setting. In another words, if missing mechanism is not MCAR, it is likely explainable by the above model covariates and response trajectory.

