## 9.4 Appendix 4: Example SAS Codes

```
/** Multiple Imputation */
proc mi data=TSS seed=1357986420 nimpute=50 out=TSS_IMPUTED1 ;
  by TRTMT ;
  mcmc chain=multiple impute=full initial=em nbiter=200 niter=100 ;
var B_EOS B_TSS TSS_W01_02 TSS_W03_04... TSS_W21_22 TSS_W23_24 ;
quit;
/** Recalculate change from baseline */
data tss_imputed2;
  set tss_imputed1;
  chg=tss_w23_24 - b_tss;
run;

proc sort data=tss_imputed2 out=tss_imputed;
  by _imputation_;
run;

/** ANCOVA by imputation */
ods output diffss=diffss lsmeans=lsm;
proc mixed data=tss_imputed method=reml;
  by _imputation_;
  class analysis center gender TRTMT;
  model CHG= analysis_center genderB_TSS TRTMT;
  lsmeans TRTMT / diff;
quit;
ods output close;

/** Combine LS Means (by treatment and difference) */
data lsmdiff;
  set lsm diffss(in=d);
  if d then trtmt='DIFF';
run;

proc sort;by TRTMT;run;

/** Synthesized results */
ods output ParameterEstimates=SYNDIF;
proc mianalyze data=LSMDIFF alpha=0.05;
  by TRTMT;
  modeleffects ESTIMATE;
  stderr;
run ;
ods output close;
```

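### The PROC MIANALYZE calls supply no complete-data degrees of freedom, so both multiple-imputation sensitivity analyses of TSS would be judged against a near-normal reference

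*SAP*

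**What the plan says.** SAP 5.4.2 imputes missing Weeks 23–24 averages by MCMC, separately in each arm, 50 times. The imputation uses 14 variables: baseline eosinophil count, baseline TSS and 12 biweekly TSS averages. Each completed data set is analysed by ANCOVA, and the pooled estimate and standard error go into the test of the treatment difference. The code is introduced by "An example of the SAS code for the synthesized LSM comparisons between treatment is as follows", and the pooling call is "proc mianalyze data=DIFF alpha=0.05".

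Three more pooling calls follow:

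- 6.11.5, Step 4 of the placebo-based pattern-mixture analysis: "proc mianalyze data=PESTIMATES". The MMRM in Step 3 requests DDFM=KR.
- 6.11.5, ANCOVA sensitivity analysis, where the text says the treatment effect is tested by an F-test. The call is the same line as in Appendix 4.
- Appendix 4 (9.4): "proc mianalyze data=LSMDIFF alpha=0.05".

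None of the four contains EDF=, and the SAP text gives no degrees-of-freedom rule for pooled results. On size, 3.5 says "A total of approximately 80 subjects will be enrolled".

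The primary symptom analysis (6.11.4) is an MMRM with DDFM=KR and has no imputation step. Section 6.12.5 imputes weekly TSS and then fits an MMRM, but shows no pooling code. Protocol 15.6.2 specifies Kenward-Roger degrees of freedom for that endpoint.

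**The concern.** PROC MIANALYZE is given only estimates and standard errors, so it cannot know the complete-data degrees of freedom. Without EDF= it treats them as infinite and uses Rubin's large-sample formula. That formula reflects the number of imputations and the share of missing information, but not the number of patients. In a trial of about 80, the pooled test then refers to something close to a normal distribution. The Kenward-Roger degrees of freedom requested in Step 3 of 6.11.5 are lost at the next step.

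The result is an ordering that should not occur: an analysis with missing data gets a looser critical value than the same analysis with complete data. Protocol 15.6.1 presents the pattern-mixture analysis as a conservative stress test of the primary MMRM. It should not use a more lenient reference distribution than the analysis it tests. At stake are the intervals and p-values of the two sensitivity analyses.

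**Working it through.** The plan states no pooled degrees of freedom or interval width, so it has no figure of its own to reproduce here.

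**Inputs**

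- Imputations m = 50 (SAP 5.4.2). Two-sided alpha 0.05 (SAP 5.8).
- N = 80, 40 per arm (SAP 3.5). The size of the Evaluable population is not given. N = 60 is an assumption, used to show the range.
- ANCOVA parameters, from the code in 6.11.5 with the five centers of 5.7: intercept 1 + gender 1 + center 4 + baseline 1 + treatment 1 = 8. Complete-data degrees of freedom are c = 80 − 8 = 72, or 60 − 8 = 52.
- Share of variance due to missing data, λ: not in the documents, assumed 0.05 to 0.30.
- SD 12.5 (SAP 3.5).

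For the MMRM, the Kenward-Roger value depends on the data. The ANCOVA value stands in for it.

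**Formulas**

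- Default: df = (m − 1)/λ².
- Barnard-Rubin: df_obs = [(c + 1)/(c + 3)] × c × (1 − λ), then 1/df = λ²/(m − 1) + 1/df_obs.

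Worked case, N = 80 and λ = 0.20: the default is 49/0.04 = 1,225. Then df_obs = (73/75) × 72 × 0.80 = 56.1, and the pooled value is 1/(1/1,225 + 1/56.1) = 53.6. The critical values are 1.9619 and 2.0052. Their ratio is 0.978, so the interval is 2.2% narrower.

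| N | λ | default df | Barnard-Rubin df | default t | Barnard-Rubin t | default narrower by |
|---|---|---|---|---|---|---|
| 80 | 0.05 | 19,600 | 66.4 | 1.960 | 1.996 | 1.8% |
| 80 | 0.20 | 1,225 | 53.6 | 1.962 | 2.005 | 2.2% |
| 80 | 0.30 | 544 | 45.0 | 1.964 | 2.014 | 2.5% |
| 60 | 0.05 | 19,600 | 47.5 | 1.960 | 2.011 | 2.5% |
| 60 | 0.20 | 1,225 | 38.8 | 1.962 | 2.023 | 3.0% |
| 60 | 0.30 | 544 | 33.0 | 1.964 | 2.035 | 3.5% |

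With no missing data, t would be 1.994 (c = 72) or 2.007 (c = 52). Every default value lies below these.

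The text of 6.11.5 names only treatment and baseline TSS. With those three parameters, c = 77 or 57, and the narrowing is 1.7–2.3% at N = 80 and 2.3–3.1% at N = 60.

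**In TSS points.** With SE = 12.5 × √(4/N)/√(1 − λ) and λ = 0.20:

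- N = 80: SE 3.13, half-width 6.13 against 6.27.
- N = 60: SE 3.61, half-width 7.08 against 7.30.

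**Does the test exceed 5%?** Null simulations used within-arm imputation with m = 50, then ANCOVA on treatment and baseline. There were 30 or 40 per arm, 10% or 20% of final values missing, and 16,000 runs per setting (Monte Carlo SE about 0.17 points). Correlations and missingness are assumed.

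| Imputation model | default df | Barnard-Rubin df |
|---|---|---|
| Baseline TSS + 2 earlier scores | 5.2–5.7% | 4.7–5.3% |
| Baseline TSS + 11 earlier scores, close to the SAP list | 4.2–5.2% | 3.7–4.9% |

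Two further simulations used all 14 variables:

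- With monotone dropout and 8,000 runs per setting, default rejection was 1.7–4.4% for within-arm imputation and 1.0–2.9% for placebo-based imputation. Barnard-Rubin gave 1.5–4.0% and 0.8–2.7%.
- With a Jeffreys-prior MCMC, 40 per arm and 10% missing gave about 5.3% against 5.0% with Barnard-Rubin. Other settings were below 5%.

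**The case against.** The strongest objection is that no harm to the error rate is shown. Taking Barnard-Rubin as exact, a reader might infer that the nominal 5% test really runs at about 5.4–5.6% at N = 80, or 5.6–5.8% at N = 60. That compares two t quantiles and ignores how the planned imputation behaves. Fitting 14 variables within about 40 patients per arm adds between-imputation variance, and with a SAP-like model the default test was mostly at or below 5%. This objection stands: undercoverage is not established.

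The reach is also limited. A reader might infer that a co-primary test is affected, but the symptom co-primary takes its degrees of freedom from the MMRM and histology uses Fisher's exact test. A reader might also count the weekly TSS secondary as another omission. Section 6.12.5 has no pooling code, so that holds only if its results are pooled in the same way.

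Finally, the code is labelled as example or sample and is visibly unfinished. Step 3 of 6.11.5 runs on `data=tss` with no BY `_imputation_`, so Step 4 would not receive per-imputation estimates whatever the degrees of freedom. That fault needs its own correction. It does not excuse the omission, because the code is the only place where pooling is specified and the text does not fill the gap.

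**Conclusion.** The point holds as a minor specification gap. All four calls omit EDF=. Followed as written, the two sensitivity analyses use a critical value of about 1.96, against about 1.99 for the same ANCOVA with complete data at N = 80. This conflicts with the SAP's own request for DDFM=KR and an F-test.

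Relative to Barnard-Rubin, intervals are about 2–2.5% narrower at N = 80 and up to about 3.5% narrower at N = 60. These sizes rest on an assumed 5–30% missing information, an assumed lower N, and the ANCOVA degrees of freedom as a stand-in for Kenward-Roger. The infinite-df default is a property of the software that the documents do not state. No conclusion about inflated type I error follows, and both co-primary tests are untouched.

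**What to change.** Add EDF= to all four PROC MIANALYZE calls: 5.4.2, both in 6.11.5, and Appendix 4. For the ANCOVA, use the residual degrees of freedom in the population analysed. For the MMRM, use the Kenward-Roger degrees of freedom of the Weeks 23–24 contrast. These may differ between imputations, so say which summary is used. State in 5.4.2 and 6.11.5 that pooled inference uses Barnard-Rubin degrees of freedom. If weekly TSS in 6.12.5 is pooled in the same way, apply the same rule there, because the protocol specifies Kenward-Roger for it.

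The cost is one option per call and a sentence of text. Intervals become about 2–3.5% wider over the range examined. Where the imputation is already conservative, the test becomes slightly more so.

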#### 5.4.3 Missing or Partial Dates of Adverse Events or Concomitant Medications

Adverse events with incomplete start or stop dates (i.e., either day or month is missing) will be considered treatment-emergent adverse events (TEAE) unless the partial start date or the stop date confirms the AE started or ended prior to Study Day 1 (e.g., the day of the AE start date is unknown but the month and year indicate that the AE starts prior to Study Day 1). Adverse

events with missing relationship to study drug will be included in the “Related” category for the summary tables and footnoted. Adverse events with missing severity will not be included in the by-severity summary table but will be footnoted in the table.

When there is incomplete information regarding dosing dates for prior and concomitant medication, the medication will be considered as a concomitant medication unless it contradicts with the stop date. For example, a medication will be considered a prior medication if the month and year of the end date indicates a date before Study Day 1 even though the start date could be missing.

## **5.5 Interim Analysis**

No interim analysis is planned.

## **5.6 Timing of Data Analyses**

The database lock will occur after all subjects complete participation in the double-blind period of the study.

For the database lock, applicable EDC data will be locked in order to protect write access after the following preconditions are fulfilled:

- All records are entered in the database.
- All AE are coded to the satisfaction of the Chief Medical Officer.
- All medications are coded to the satisfaction of the Chief Medical Officer.
- All data queries have been resolved.
- All decisions have been made regarding all protocol violations and ITT population exclusions.
- Written authorizations to lock the database are obtained from Allakos Clinical Data Management and the Chief Medical Officer.

The randomization code for this study will not be revealed until the previous preconditions are fulfilled, and documentation of the database lock is complete. After the database lock, the randomization code will be made available to individuals at Allakos who are involved in the data analysis. Data analysis will commence after the data lock. In addition, the PK and ADA data may be locked and assessed separately.

## **5.7 Multicenter Study**

The study will have approximately 35 sites. Analysis of site effect will be based on analysis centers. Analysis centers will be formed in such a way that there are sufficient subjects per

pooled analysis center for the assessment of study site effects. Pooling of study sites by geographic location is described below:

- **Analysis Center 1:** Massachusetts, Connecticut, Rhode Island, New York, New Jersey, Pennsylvania, District of Columbia, Maryland, Maine, Vermont, Delaware, and New Hampshire
- **Analysis Center 2:** Virginia, West Virginia, South Carolina, Georgia, Mississippi, Florida, Alabama, Louisiana
- **Analysis Center 3:** North Carolina, Tennessee, Ohio, Michigan, Indiana, Kentucky
- **Analysis Center 4:** South Dakota, Arkansas, Minnesota, Wisconsin, North Dakota, Illinois, Missouri, Iowa, Texas, Oklahoma, Kansas, Nebraska, Wyoming, Colorado
- **Analysis Center 5:** Utah, New Mexico, Arizona, California, Oregon, Washington, Idaho, Hawaii, Alaska, Montana, Nevada

## 5.8 Multiple Comparisons/Multiplicity Adjustment

To control for the family-wise type-I error rate, the following testing procedures will be implemented:

Test each co-primary efficacy endpoint at 2-sided  $\alpha=0.05$  level.

- If  $p \leq 0.05$  for both co-primary endpoints, then reject the null hypothesis that AK002 is no different from placebo and accept the alternative hypothesis that AK002 is superior to placebo in reducing tissue eosinophil count and TSS score.
- If  $p \leq 0.05$  for both co-primary endpoints, the hypothesis tests for the secondary endpoints will proceed in the prespecified order.
- If  $p > 0.05$  for either co-primary endpoint, the null hypothesis is accepted. No hypothesis test will be performed for the secondary endpoints.
- The issue of multiplicity of secondary endpoints will be handled by statistical testing of these outcomes in a hierarchical fashion. The order of secondary endpoints is described in Section 2.2. If at any point during the analysis of the secondary endpoints, the statistical test is not significant at 2-sided  $\alpha=0.05$  level, the hypothesis testing procedure will stop. AK002 will be deemed superior to placebo for all endpoints prior to the stop.

## 5.9 Examination of Subgroups

Key endpoints will be summarized by subgroup to assess the consistency of the treatment effect across subgroups. Subgroups to be considered are:

- Gender (Male, Female)
- Age (<65,  $\geq$ 65)
- Race (White, Non-White)
- IgE (<45,  $\geq$ 45)

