#### 6.1.5 Primary Analysis Population

The primary efficacy analysis population is the Evaluable Population defined as all randomized subjects who have received at least 1 infusion of study drug, and at study entry do not exhibit any of the following criteria:

1.  $>6$  eosinophils per hpf in at least one esophageal biopsy at baseline
2. Documented history of irritable bowel syndrome and baseline diarrhea intensity  $\geq 3$ .

- The complement to the Evaluable population will be referred to as the Excluded population. It is worth remarking that for this study, if a subject has a history of concomitant EoE, or if

esophagus looks suspicious for EoE or other condition, or if patient is symptomatic on screening dysphagia question, quantified by a score of  $>3$  on the dysphagia question on at least 1 day during screening, then the following is undertaken:

- A set of 2 fragments is collected from the distal esophagus
- A set of 2 fragments is collected from the mid-proximal esophagus
- Up to 2 extra specimens may be collected if there are any additional areas of interest.
- A count of  $>6$  eosinophils per hpf in at least one esophageal site will be considered diagnostic of at least having esophageal eosinophilia for the purposes of the study and in cases where there is a history of EoE this could reflect active eosinophilic esophagitis although fulfillment of the diagnostic criteria for that condition may not be certain (see Appendix 5 for details).

Analysis will be conducted on the complement population, referred to as Excluded Population, and is planned as exploratory. In addition, for completeness purposes, analysis will be conducted on the mITT population to show what the study results would have been on all the subjects prior to removing those with confounding conditions outlined above.

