## 6.11.3 Subgroup Analysis of the First Co-primary Endpoint

Analysis comparing AK002 and placebo will use the Fisher's exact test for each of the subgroups defined in Section 5.9.

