## 6.11.6 Supplementary Analyses

Analysis of Section 6.11.2 will be repeated for the Per Protocol population.

Additional analysis will investigate the treatment effect on PRO TSS change from baseline in the subgroups defined in Section 5.9. This analysis will use MMRM similarly to the primary analysis (Section 6.11.2).

Empirical cumulative distribution function (eCDF) of the change from baseline in TSS will be plotted by treatment group to demonstrate consistency of the treatment effect.

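### The subgroup analyses are meant to assess consistency of the treatment effect, but no contrast between subgroup levels is planned

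*SAP*

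**What the plan says.** SAP 5.9 lists gender, age (<65, ≥65), race (White, Non-White) and IgE (<45, ≥45), and states the aim: "Key endpoints will be summarized by subgroup to assess the consistency of the treatment effect across subgroups".

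For the histology co-primary, SAP 6.11.3 says: "Analysis comparing AK002 and placebo will use the Fisher's exact test for each of the subgroups defined in Section 5.9". For TSS, SAP 6.11.6 says: "Additional analysis will investigate the treatment effect on PRO TSS change from baseline in the subgroups defined in Section 5.9", using an MMRM like the primary analysis. The primary MMRM in 6.11.4 has treatment, period, baseline TSS, gender and pooled site, with treatment-by-period and baseline-by-period interactions. It has no treatment-by-subgroup term. The table list in SAP Appendix 3 has one histology table and one TSS MMRM table per factor. Protocol 15.4 says only that subgroup analysis will be done.

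Neither document specifies an interaction term, a heterogeneity test, or a difference between subgroup effects with a confidence interval. Neither says that consistency will be decided by whether each level reaches p ≤ 0.05.

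**The concern.** Consistency concerns the null hypothesis that the AK002-placebo difference is the same in both levels of a factor. A comparison within one level tests a different null: that the difference in that level is zero. Its p-value depends on the size of the level as well as on the effect there. When the two levels are small or unequal, an identical true effect readily gives p ≤ 0.05 in one and p > 0.05 in the other.

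With about 80 patients in total, most levels will be small. If the within-level p-values are the material from which consistency is read, a uniform effect could be reported as confined to the larger level, for example under 65 but not at 65 or over. The quantity that answers the SAP's question, the difference between the two levels' effects with its uncertainty, would not be in the report.

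**Working it through.** **Inputs from SAP 3.5.** "A total of approximately 80 subjects will be enrolled"; "A sample size of approximately 40 patients per treatment group will provide 80% power". The target difference is 7.4 points and the common SD is 12.5. Allocation is 1:1 and tests are two-sided at 0.05. Histologic response is assumed to be 0.6 versus 0.1.

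**Assumptions not in the documents.** Level splits from 50/50 to 90/10, equal in both arms; 40 per arm, or 32 per arm if the Evaluable population is smaller; no dropout; a two-sample t comparison standing in for the MMRM.

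**The plan's own figure.** With n = 40, noncentrality = 7.4 / (12.5 × √(2/40)) = 7.4 / 2.795 = 2.65. Power is 74.4% by noncentral t (75.4% by normal approximation), not the stated 80%. This is a separate matter. If the true difference were 7.83, which does give 80% by normal approximation, the even-split result below would be 50.0%, essentially the same.

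**Discordance under a uniform effect.** Let pA and pB be the powers in the two levels with the same true effect. The chance that exactly one is significant is

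pA(1 − pB) + pB(1 − pA).

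Even split at 40 per arm: 20 per arm in each level, power 0.446 each, so 2 × 0.446 × 0.554 = 0.494.

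| Split | 40 per arm: pA, pB | Discordant | 32 per arm: pA, pB | Discordant |
|---|---|---|---|---|
| 50/50 | 0.446, 0.446 | 49% | 0.367, 0.367 | 47% |
| 70/30 | 0.585, 0.284 | 54% | 0.491, 0.232 | 49% |
| 80/20 | 0.645, 0.197 | 59% | 0.546, 0.162 | 53% |
| 90/10 | 0.697, 0.110 | 65% | 0.598, 0.092 | 58% |

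**Dependence on the true effect** (even split, 40 per arm): 20% at 3 points, 36% at 5, 49% at 7.4, 27% at 12. For an even split, 2p(1 − p) cannot exceed 50%, and 7.4 points sits close to that maximum.

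**Interaction contrast under the same uniform effect.** Simulated rejection is 4.7–5.5% per factor with even splits (4,000 trials). Over four evenly split factors, at least one interaction signal occurs in about 19% of trials and at least one discordant pair in about 81%.

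**Precision of the contrast.** SE of the difference between two level effects = 12.5 × √(2/nA + 2/nB). With 20 per arm in each level this is 12.5 × √0.2 = 5.59 points, so the 95% CI half-width is about 1.99 × 5.59 = 11.1 points. Power for a 10-versus-0-point difference is about 42% (even split, 40 per arm), falling to roughly 15% (90/10, 32 per arm).

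**Histology in small levels.** With 3 per arm the most extreme table gives a two-sided Fisher p of 0.10, so rejection is impossible. At 0.6 versus 0.1, exact power is 8.5% at 4 per arm and 39% at 8. At the rates Protocol Table 1 reports for the preceding Phase 3 study (84.6% versus 4.5%, in a broader EG/EoD population), it is 43% and 94%.

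**The case against.** The best defence is that SAP 5.9 speaks of summarising by subgroup and sets no decision rule. Subgroups also lie outside the testing hierarchy in SAP 5.8. That stands: the discordance rates describe what happens if p-values are used as the yardstick, not what the SAP commits to.

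Second, much of the useful output is probably planned already. The primary MMRM code requests confidence limits, and the code in 6.11.1 gives an exact interval for the risk difference, so level-specific estimates with intervals would follow naturally. That also stands. It narrows the gap to the between-level difference, which nothing supplies.

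Third, the 5% for the interaction test is its nominal level by construction, and the test is weak here. That is true, and it is why the remedy is an estimate with an interval rather than another p-value.

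Three stronger readings are tempting but not supported:

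- A reader might infer that the consistency answer would be wrong more often than not. For a single factor, that needs an uneven split and an effect near 7.4 points. It fails for even splits and for several other effect sizes, and the documents give no subgroup proportions.
- A reader might infer that the TSS model cannot be estimated in a small level because the unstructured covariance matrix is too large. SAP 6.11.4 provides Toeplitz, autoregressive and compound-symmetry fallbacks. Nor does the text state outright that each level gets its own fit.
- A reader might infer that a non-significant result in the Excluded population would be taken to confirm the population restriction. SAP 4.2.1 bases the restriction on AK002-016 data. On the complement, SAP 6.1.5 says "Analysis will be conducted on the complement population, referred to as Excluded Population, and is planned as exploratory", and it adds an mITT analysis of all dosed patients.

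**Conclusion.** The concern holds in a limited form. The specified comparisons do not address the question that SAP 5.9 sets, because no contrast between levels is planned. At the SAP's TSS assumptions, reading consistency from within-level p-values would show a discordant pair in about 47–65% of trials with a uniform effect (32–40 per arm, assumed splits 50/50 to 90/10), against about 5% per factor for an interaction contrast. With an even split at 40 per arm, discordance is about 20–36% if the true effect is 3, 5 or 12 points. These figures rest on the assumed splits and population sizes and on a simple two-sample approximation to the MMRM.

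The consequence is confined to supportive subgroup statements. The co-primary tests, the ordered secondary tests and their error control are unaffected. The change is worth making because it supplies the missing quantity at almost no cost.

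**What to change.** Amend SAP 5.9, 6.11.3 and 6.11.6.

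- **TSS:** for each factor, fit one MMRM on the Evaluable population with subgroup, subgroup-by-period, treatment-by-subgroup and treatment-by-subgroup-by-period terms and a common covariance structure. Report the Weeks 23–24 treatment effect with 95% CI in each level, and the difference between levels with its 95% CI.
- **Histology:** report the risk difference with 95% CI in each level, and the difference between the two risk differences with its CI.
- **Interpretation:** state that consistency is judged from the between-level contrast and its interval, and that any within-subgroup p-values are descriptive.
- **Optional:** within the mITT analysis already planned, report the same contrast for Evaluable versus Excluded.

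The same edit can correct the cross-reference in 6.11.6, which cites 6.11.2 (the CMH sensitivity analysis) as the primary MMRM; that model is in 6.11.4.

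The cost is SAP wording, some model terms and a few table rows, with no new data. The three- and four-way terms are not small for at most 80 patients: with 12 two-week periods, the subgroup terms add about 24 fixed-effect parameters per two-level factor. The contrasts will be imprecise, with roughly 15–42% power for a 10-versus-0-point difference, and the intervals will show this openly.
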